## Statistical Analysis Plan

```
PROC NPAR1WAY DATA=... hl;  
* hl adds Hodges-Lehmann confidence interval for delta;  
CLASS treatment;  
VAR time;  
RUN;
```

### **6.3.12.1.10 Normal breathing patients within 24 hours**

Percentage of patients with normal breathing within 24 hours will be compared by treatment groups by means of a Fisher's exact test at 5% significance interval. Odds ratio (OR) and related exact 95% CI will be also provided.

The median duration time to reach FiO2 equal to 0.21 will be compared between treatments by the Mann-Whitney U-test.

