8. EFFICACY ASSESSMENTS

- SpO₂/FiO₂ at 30 minutes, at 1, 3, 6, 12, 18, 24 hours, at Days 2, 3, 5, 7, 28±2 PNA, at discharge home and at 36 weeks PMA.

- Fraction of inspired oxygen (FiO₂) at 30 minutes, at 1, 3, 6, 12, 18, 24 hours, at Days 2, 3, 5, 7, 28±2 PNA, at discharge home and at 36 weeks PMA;
- Respiratory Severity Score (RSS) will be calculated from ventilator setting as FiO₂ x MAP in the 2 days post treatment (at 30 minutes, at 1, 3, 6, 12, 18, 24 hours and on day 2);
- Oxygen Saturation Index (OSI) will be calculated as FiO₂ x MAP x 100 / SpO₂ in the 2 days post treatment (at 30 minutes, at 1, 3, 6, 12, 18, 24 hours and on day 2);
- Arterial oxygen saturation determined by pulse oximetry (SpO₂) at 30 minutes, at 1, 3, 6, 12, 18, 24 hours, at Days 2, 3, 5, 7, 28±2 PNA, at discharge home and at 36 weeks PMA;
- Mean airway pressure (MAP) at 30 minutes, at 1, 3, 6, 12, 18, 24 hours, on Days 2, 3, 5, 7;
- Peak inspiratory pressure (PIP) at 30 minutes, at 1, 3, 6, 12, 18, 24 hours, on Days 2, 3, 5, 7;
- Positive end-expiratory pressure (PEEP) at 30 minutes, at 1, 3, 6, 12, 18, 24 hours, on Days 2, 3, 5, 7
- Alveolar-arterial (A-a) at 3, 6, 12, 18, 24 hours and 2 days post treatment (only in a subgroup of babies when feasible).
- Oxygenation Index (OI) at 3, 6, 12, 18, 24 hours and 2 days post treatment (only in a subgroup of babies when feasible).
- Mortality/BPD rate defined as the incidence of patients who are dead or alive with a diagnosis of BPD at 36-week PMA;
- BPD incidence at 36-week PMA;
- Mortality rate at Day 28 PNA and 36-week PMA;
- RDS-associated mortality rate through 14 days of age, defined as deaths associated with RDS through the first 14 days of life, resulting from severe respiratory failure, from pulmonary hemorrhage if the RDS had not resolved before the development of this complication, or from air leaks that occurred in the presence of severe RDS;
- Percentage of patients requiring at least one surfactant rescue dose;
- Percentage of patients with at least one reading of FiO₂=0.21 (i.e. room air) within 24 hours from first dosing with test treatment;
- Time (hours) to reach FiO₂=0.21 (i.e. room air);
- Duration of invasive mechanical ventilation, defined as the time until the first successful extubation lasting more than 24 hours (days);

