12.3.4 Efficacy variables

Arterial Oxygen Saturation and Ventilator settings

SpO₂/FiO₂

- SpO₂/FiO₂ will be analyzed using a linear mixed model for repeated measures (MMRM) including treatment, time point, treatment by time point interaction, investigational site and gestational age group as fixed effects and pre-dose SpO₂/FiO₂ as covariate. The adjusted means in each treatment group, the adjusted mean difference between treatments and their 95% confidence intervals (CIs) at each time point and averaged over the first 24 hours will be estimated by the model.

Time profile plot of mean SpO₂/FiO₂ in the first 24 hours post-treatment will be presented by treatment group.

- SpO₂/FiO₂ will be compared between treatments at the remaining post-treatment time points (i.e., Days 2, 3, 5, 7, 28±2 PNA, at discharge home and at 36 weeks PMA) using mixed model including treatment, investigational site and gestational age group as fixed effects and pre-dose SpO₂/FiO₂ as covariate.
- SpO₂/FiO₂ will be analyzed by subgroups based on ventilator support used.

FiO₂

➤ FiO₂ will be analyzed at each time point and averaged over the first 24 hours post dose using the same model used for the SpO₂/FiO₂. Pre-dose FiO₂ will be used as covariate.

Time profile plot of mean FiO₂ in the first 24 hours after treatment will be presented by treatment group.

- FiO₂ will be compared between treatments at the remaining post-treatment time points (i.e., Days 2, 3, 5, 7, 28±2 PNA, at discharge home and at 36 weeks PMA) using linear mixed model including, treatment, investigational site and gestational age group as fixed effects and pre-dose FiO₂ as covariate.
- Percentage of patients with at least one reading of FiO₂ equal to 0.21 (i.e. at room air) within 24 hours from first intake will be compared by treatment group by means of a Fisher's exact test at 5% significance interval. Odds Ratio (OR) and related exact 95% CI will be also provided.
- The median duration time to reach FiO₂ equal to 0.21 will be compared between treatment groups by the Mann-Whitney U-test.

Respiratory Severity Score

- RSS, calculated from ventilator settings as MAP x FiO₂, will be analyzed at each time point and averaged over the first 24 hours post study drug intake using the same model used for the SpO₂/FiO₂.

Time profile plot of mean RSS in the first 24 hours after treatment will be presented by treatment group.

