### ***6.1.4.12 Normal breathing (i.e. at room air) patients within 24 hours***

Percentage of patients with at least one reading of FiO2 equal to 0.21 (i.e. at room air) within 24 hours from first intake will be taken as estimation of normal breathing.

Additionally the median duration time to reach FiO2 equal to 0.21 (normal breathing) will be determined.

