### 6.3.4 Missing Data

Generally there will be no imputation of missing data. Hence critical missing data, if any, will be discussed during the BDRM before database lock. Decisions will be fully documented in the BDRM Report.

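### Time to room air is compared by Mann-Whitney with no window and no rule for babies who never reach FiO2 0.21, so as written only reachers are compared

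*SAP*

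**What the plan says.** Time in hours to FiO2 0.21 is a listed efficacy variable (Protocol 8). Protocol 12.3.4 says that the median time to an FiO2 "equal to 0.21 will be compared between treatment groups by the Mann-Whitney U-test", and SAP 6.3.12.1.10 repeats this ("equal to 0.21 will be compared between treatments by the Mann-Whitney U-test"). The definition in SAP 6.1.4.12 adds only that the median time to an FiO2 "equal to 0.21 (normal breathing) will be determined".

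The 24-hour limit in the text belongs to a different variable. In SAP 6.1.4.12 it is the percentage of babies with a 0.21 reading "within 24 hours from first intake will be taken as estimation of normal breathing", and SAP 6.3.12.1.10 tests that percentage by Fisher's exact test: "Percentage of patients with normal breathing within 24 hours will be compared by treatment groups". The time variable shares only the section headings. FiO2 itself is also recorded "at Days 2, 3, 5, 7, 28±2 PNA, at discharge home and at 36 weeks PMA" (Protocol 8).

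On missing values, SAP 6.3.4 says: "Generally there will be no imputation of missing data. Hence critical missing data, if any, will be discussed during the BDRM before database lock". The only Mann-Whitney code, given for the durations in SAP 6.3.12.1.9, has a treatment class and one time variable, with no status variable.

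**The concern.** Non-reachers are to be expected. Babies enter needing FiO2 of at least 0.30 or 0.35, according to gestational age (Protocol 4.2), and the companion percentage presupposes that some are not at room air by 24 hours. A baby who stays on oxygen or dies first has no time to 0.21. With no rank, no censoring and no imputation, that baby leaves the test.

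The comparison is then restricted to a group defined by response after treatment, and randomisation no longer protects it. If one surfactant brings more babies to room air, and the additional ones are slower cases, the better arm's reachers look slower. The report could then carry a significant p-value pointing the wrong way. The SAP writes comparable rules elsewhere: values for biomarkers outside the quantification limits (6.3.12.1.11), exclusion of unassessed BPD cases (6.3.12.1.7), and unknown start and end times for ventilation and oxygen (6.1.4.10, 6.1.4.11).

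**Working it through.** **Inputs from the documents.** 63 babies per arm (SAP 4); two-sided 5% tests (SAP 6.3.2); readings at 0.5, 1, 3, 6, 12, 18 and 24 h and on Days 2, 3, 5 and 7, taken as 48, 72, 120 and 168 h (Protocol 8). The plan gives no reaching rate, effect size or power, so there is no figure to reproduce.

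**Assumed inputs.** Reaching times log-normal, median 6 h, log-SD 1. In the late scenarios the better arm has the same early reachers as the worse arm plus extra reachers with median 36 h and log-SD s of 1 or 0.5.

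**Step 1: what a reachers-only test measures.** It compares with 0.5 the quantity θ, the probability that a better-arm reacher takes longer than a worse-arm reacher (ties count half). If times among reachers are equally distributed, θ = 0.5 whatever the two reaching rates are, so the test has no power against a difference in rates.

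**Step 2: late extra reachers, 80% v 50%, by hand.** Of the better arm's reachers, 50/80 = 0.625 are early and 0.375 late.

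- Probability that a late time exceeds an early one: q = Φ(ln(36/6)/√(1 + s²)), which is Φ(1.792/1.414) = 0.897 for s = 1 and Φ(1.792/1.118) = 0.945 for s = 0.5.
- θ = 0.625 × 0.5 + 0.375 × q = 0.649 or 0.667.
- Reachers: m = 63 × 0.8 = 50.4 and n = 63 × 0.5 = 31.5. Null SE = √((m + n + 1)/(12mn)) = 0.066.
- z = (θ − 0.5)/SE = 2.26 or 2.53. The chance of a significant result for the worse arm is about Φ(z − 1.96) = 62% or 72%, ignoring the reading grid and the cut at day 7.
- With all babies kept and non-reachers tied worst, the better arm wins with probability 0.8 × 0.5 × (1 − 0.649) + 0.8 × 0.5 + ½ × 0.2 × 0.5 = 0.590 (s = 1), so the direction is right.

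**Step 3: simulation.** 4,000 trials per scenario, times rounded up to the reading grid and cut at 168 h or 24 h. Ranges run over the two values of s. The log-rank test was unstratified and no deaths were modelled.

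| Better v worse arm | Reachers-only, significant for worse arm, to day 7 | Same, 24 h window | Log-rank for better arm, day 7 | Worst-rank Mann-Whitney for better arm, day 7 | Fisher at 24 h for better arm |
|---|---|---|---|---|---|
| Late, 80% v 50% | 58-75% | 10-11% | 72-74% | 39-40% | 8-18% |
| Late, 75% v 55% | 34-45% | 7% | 38-39% | 18-19% | 6-10% |
| Late, 80% v 70% and 70% v 60% | 12-17% | 4% | | | |
| Late, 95% v 90% | 5-6% | 2-3% | | | |

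The nominal figure for the two reachers-only columns is 2.5%. With equal times and 80% v 50% to day 7, the reachers-only test rejects in 5%, log-rank in 94% and Fisher at 24 h in 87%.

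**Step 4: a 24-hour window under other assumptions.** A separate simulation used only the readings to 24 h, with 60% v 40%, 70% v 50% and 50% v 30% reaching by then. About 50 to 76 of the 126 babies enter a reachers-only test. With equal times it rejects in 4.7-4.9%, against 53-59% with non-reachers ranked worst. When the extra reachers arrive at 12 to 24 h, it significantly favours the worse arm in 34-42%. The low 24-hour figures in Step 3 arise largely because extra reachers with a 36 h median mostly fall outside that window.

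**The case against.** Neither document says that non-reachers are excluded. A baby still on oxygen has observed FiO2 readings, efficacy is analysed in the ITT population, and the blind data review could have set a rule. A 24-hour window is a natural reading: both SAP headings and the title of Table 14.2.2.4 say so, and the unit is hours. The largest figures need a day 7 cut that the documents never name, differences of 20 to 30 points, and extra reachers who are all late. At 24 h in those scenarios, log-rank does little better than Fisher (8-16% for 80% v 50% and 5-10% for 75% v 55%, from 2,000 trials each). The study is exploratory, and the 24-hour mixed models of SpO2/FiO2 and FiO2 keep babies still on oxygen.

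Much of this stands as a limit on size. Exclusion is an inference, the inputs are assumptions, and Fisher covers a difference that appears by 24 h. It does not close the gap. Naming the ITT set does not give a non-reacher a time, and a 24-hour window would still leave every baby not at 0.21 by then without a value. A separate Fisher result does not correct a time test that points the other way.

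**Conclusion.** The concern holds. The rule for non-reachers and for deaths before room air is absent, and the written rules lead to a test among reachers only. That such a test is blind to the share reaching room air follows from its construction and needs no assumed rates. The risk of a significant result for the worse arm does depend on assumptions. With late extra reachers to day 7 it runs from 5-6% (95% v 90%) to 58-75% (80% v 50%). With a 24-hour window it is 2-11% if the extra reachers have a 36 h median, and 34-42% if they arrive at 12 to 24 h with 20-point differences. The endpoint is supportive, so this should be fixed but does not undermine the main analyses.

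**What to change.** In SAP 6.1.4.12 and 6.3.12.1.10, state one observation window for the time variable (for example 168 h) and include all ITT babies. Name one analysis in advance: Kaplan-Meier curves with a log-rank test stratified by gestational age group. Keep non-reachers, including deaths before room air, as not having reached 0.21 up to the end of the window.

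Mann-Whitney with all non-reachers tied at the worst rank is an acceptable alternative. It is not equivalent, because it has less power for late differences (39-40% against 72-74% in the first late scenario), so the choice should not be left open. Report a median for an arm only if at least half of its babies reach 0.21.

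The cost is SAP wording and standard code. The FiO2 readings are already collected.

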### **6.3.12.1.11 Biomarkers of inflammation**

Mean values of biomarkers of inflammation (i.e., CXCL8, IL1 $\beta$ , IL6, TNF- $\alpha$ , MPO) in the tracheal aspirates as well as change from baseline to 24 hours and on Day 2 (48 hours) will be summarized by treatment by means of descriptive statistics. Additionally, total proteins concentration and CXCL8/total protein, IL1 $\beta$ /total protein, IL6/total protein, TNF- $\alpha$ /total protein, MPO /total protein will also been included.

Biomarker values below/above the limit of quantification (BLQ/ALQ) will be imputed as follows:

- 1) BLOQ (Dil), Bad Replicate (BR) and Insufficient Volume (IV) will be considered as missing
- 2) BLOQ will be imputed by the value of low detection limit divided by 2 (Example: if the database contains a value like 0.917, 0.459 value will be imputed).
- 3) ALQ by the value of detection limit plus one unit. Since diluted values have been used the following will apply

IL6 ALQ value will be imputed with 27001 (i.e. 270\*100+1)

IL8 ALQ value will be imputed with 20201 (i.e. 202\*100+1)

MPO ALQ value will be imputed with 12400001 (i.e. 24800\*500+1)

## Statistical Analysis Plan

### **6.3.12.1.12 Alveolar–Arterial Gradient**

The alveolar–arterial gradient (A-aO2) values as well as change from baseline in the first 48 hours after the first surfactant intake (i.e., at 3, 6, 12, 18, 24 hours and on Day 2) will be summarized by treatment by means of descriptive statistics.

### **6.3.12.1.13 Oxygenation Index**

The Oxygenation Index (OI) values as well as change from baseline in the first 48 hours after the first surfactant intake (i.e., at 3, 6, 12, 18, 24 hours and on Day 2) will be summarized by treatment by means of descriptive statistics.

Chiesi

Final 1.0

CCD-5633AA1-02

18/July/2018

---

TP-EP.BS-WW-001-05

Effective date: 29 Jul 15

Related to: SOP-EP.BS-WW-002

Page 36 of 46

## Statistical Analysis Plan

### 8. TABLES AND LISTINGS TO BE INCLUDED IN SECTION 14 OF THE CLINICAL STUDY REPORT

All the Tables, Figures and Listings with asterisk will be included in the Key First Results package.

#### DISPOSITION AND DEMOGRAPHIC DATA

Table 14.1.1.1 Patient Disposition (All Screened)

\*Table 14.1.1.2 Patient Disposition:(All Randomized )

Table 14.1.1.5 Major Protocol Deviations (ITT population)

Table 14.1.1.6 Minor Protocol Deviations (ITT population)

\*Table 14.1.1.7 Summary of Analysis Sets (All Randomized)

\*Table 14.1.2.1 Demographic Characteristics (ITT Population)

\*Table 14.1.2.2 Demographic Characteristics (Safety Population)

Table 14.1.4.1 Chest x-Ray (Safety Population)

Table 14.1.4.2 Complications of Prematurity at Baseline (Safety Population)

Table 14.1.5.1 Mother Medical and Surgical History (Safety Population)

Table 14.1.5.2 Pregnancy History (Safety Population)

Table 14.1.6.1 Mother Previous and Concomitant Medication (Safety Population)

Table 14.1.6.2 Neonatal Concomitant Medication (Safety Population)

Table 14.1.7.1 Cranial Sonography at Screening (Safety Population)

\*Table 14.1.8.1 Treatment Exposure (Safety Population)

#### EFFICACY DATA

\*Table 14.2.1.1.1 Summary of Ratio of Arterial Oxygen Saturation (SpO2/FiO2) versus Time Point by Treatment (ITT Population)

Table 14.2.1.1.2 Summary of Ratio of Arterial Oxygen Saturation (SpO2/FiO2) versus Time Point by Treatment (PP Population)

Chiesi

Final 1.0

CCD-5633AA1-02

18/July/2018

## Statistical Analysis Plan

\*Table 14.2.1.2.1 Statistical Analysis of the Arterial Oxygen Saturation (SpO2/FiO2) ratio in the First 24 hrs (ITT Population)

Table 14.2.1.2.2 Statistical Analysis of the Arterial Oxygen Saturation (SpO2/FiO2) ratio in the First 24 hrs (PP Population)

Table 14.2.1.3.1 Statistical Analysis of the Arterial Oxygen Saturation (SpO2/FiO2) Ratio – Additional Timepoints (ITT Population)

Table 14.2.1.3.2 Statistical Analysis of the Arterial Oxygen Saturation (SpO2/FiO2) Ratio – Additional Timepoints (PP Population)

\*Table 14.2.2.1.1 Summary of Fraction of inspired oxygen (FiO2, %) versus Time Point by Treatment (ITT Population)

Table 14.2.2.1.2 Summary of Fraction of inspired oxygen (FiO2, %) versus Time Point by Treatment (PP Population)

\*Table 14.2.2.2.1 Statistical Analysis of FiO2 (%) in the First 24 hrs (ITT Population)

Table 14.2.2.2.2 Statistical Analysis of FiO2 (%) in the First 24 hrs (PP Population)

Table 14.2.2.3.1 Statistical Analysis of FiO2 (%) – Additional Timepoints (ITT Population)

Table 14.2.2.3.2 Statistical Analysis of FiO2 (%) – Additional Timepoints (PP Population)

Table 14.2.2.4 Normal Breathing (i.e. at room air) Patients within 24 hours (ITT Population)

Table 14.2.3.1 Summary of Respiratory Severity Score (RSS) versus Time Point by Treatment (ITT Population)

Table 14.2.3.2 Statistical Analysis of the RSS in the First 24 hrs (ITT Population)

Table 14.2.3.3 Statistical Analysis of the RSS – Additional Timepoints (ITT Population)

Table 14.2.4.1 Summary of Oxygen Saturation Index (OSI) versus Time Point by Treatment (ITT Population)

Table 14.2.4.2 Statistical Analysis of the OSI in the First 24 hrs (ITT Population)

Table 14.2.4.3 Statistical Analysis of the OSI – Additional Timepoints (ITT Population)

Chiesi

Final 1.0

CCD-5633AA1-02

18/July/2018

---

TP-EP.BS-WW-001-05

Effective date: 29 Jul 15

Related to: SOP-EP.BS-WW-002

Page 39 of 46

## Statistical Analysis Plan

\*Table 14.2.5 Summary of SpO2 (%) versus Time Point by Treatment (ITT Population)

Table 14.2.6 Summary of Ventilator Settings (MAP, PIP, PEEP) versus Time Point by Treatment (ITT Population)

\*Table 14.2.7 Mortality and BPD (ITT Population)

\*Table 14.2.8 Rescue Medication (ITT Population)

Table 14.2.9 Duration of Ventilation (ITT Population)

Table 14.2.10 Summary of Duration of Oxygen Use (ITT Population)

Table 14.2.11 Biomarkers (ITT Population)

Table 14.2.12 Summary of Alveolar-Arterial Gradient (A-aO2) (ITT Population)

Table 14.2.13 Summary of Oxygenation Index (OI) (ITT Population)

## SAFETY DATA

### *ADVERSE EVENTS*

\*Table 14.3.1.3.1 Summary of Treatment-Emergent Adverse Events (Safety Population)

\*Table 14.3.1.3.2 Treatment-emergent Adverse Events by Treatment, System Organ Class and Preferred Term (Safety Population)

Table 14.3.1.3.3 Adverse Drug Reactions by Treatment, System Organ Class and Preferred Term (Safety Population)

\*Table 14.3.1.3.4 Serious AEs by Treatment, System Organ Class and Preferred Term (Safety Population)

Table 14.3.1.3.5 Neonatal Morbidities (Safety Population)

### *VITAL SIGNS*

Table 14.3.4.1 Vital Signs: Actual Values and Changes from Baseline (Safety Population)

## FIGURES

\*Figure 14.2.1 Mean (+/-95% CI) for SpO2/FiO2 ratio by Time and Treatment

Chiesi

Final 1.0

CCD-5633AA1-02

18/July/2018

---

TP-EP.BS-WW-001-05

Effective date: 29 Jul 15

Related to: SOP-EP.BS-WW-002

Page 40 of 46

## Statistical Analysis Plan

\*Figure 14.2.2 Mean (+/-95% CI) for Fraction of Inspired Oxygen by Time and Treatment

Figure 14.2.3 Mean (+/-95% CI) for Respiratory Severity Score by Time and Treatment

Figure 14.2.4 Mean (+/-95% CI) for Oxygen Saturation Index by Time and Treatment

Figure 14.2.5 Mean (+/-95% CI) for Arterial Oxygen Saturation (SpO2) by Time and Treatment

Figure 14.2.6 Mean (+/-95% CI) for MAP by Time and Treatment

## Statistical Analysis Plan

### **9. LISTINGS TO BE INCLUDED IN SECTION 16 OF THE CLINICAL STUDY REPORT**

#### **RANDOMIZATION SCHEDULE**

Listing 16.1.7 Randomization Schedule (All Randomized)

#### **SUBJECT DISPOSITION**

Listing 16.2.1.1 Screening Failures (All Enrolled)

Listing 16.2.1.3. Study Discontinuation (All Randomized)

Listing 16.2.1.4 Study Visit dates (All Randomized)

Listing 16.2.1.5 Study Kits Details (All Randomized)

#### **PROTOCOL DEVIATIONS**

Listing 16.2.2.1: Major Protocol Deviations (All Randomized)

Listing 16.2.2.2: Minor Protocol Deviations (All Randomized)

Listing 16.2.2.3 Violation of Inclusion/Exclusion Criteria (All Randomized)

#### **ANALYSIS POPULATIONS**

Listing 16.2.3.1 Population Disposition (All Randomized)

#### **DEMOGRAPHICS AND OTHER BASELINE CHARACTERISTICS**

Listing 16.2.4.1 Demographic Characteristics (All Randomized)

Listing 16.2.4.2 Complications of Prematurity (All Randomized)

Listing 16.2.4.3 Chest X-Ray (All Randomized)

Listing 16.2.4.4 Cranial Sonography (All Randomized)

Listing 16.2.4.5.1 Mother Medical and Surgical History (All Randomized)

Listing 16.2.4.5.2 Pregnancy History (All Randomized)

Listing 16.2.4.6.1 Mother Previous and Concomitant Medication (All Randomized)

Chiesi

Final 1.0

CCD-5633AA1-02

18/July/2018

---

TP-EP.BS-WW-001-05

Effective date: 29 Jul 15

Related to: SOP-EP.BS-WW-002

Page 42 of 46

## Statistical Analysis Plan

Listing 16.2.4.6.2 Neonatal Concomitant Medications (All Randomized)

### **COMPLIANCE AND/OR DRUG CONCENTRATION DATA**

Listing 16.2.5.1 Study Medication Administration (All Randomized)

Listing 16.2.5.2 Hospital Transfer (All Randomized)

Listing 16.2.5.3 Breaking the Blind (All Randomized)

### **EFFICACY/PHARMACODYNAMIC DATA**

Listing 16.2.6.1 Arterial Oxygen Saturation (SpO2), Fraction of Inspired Oxygen (FiO2), SPO2/FiO2 (All Randomized)

Listing 16.2.6.2 Ventilator Settings and Respiratory Parameters (PIP, MAP, PEEP, RSS, OSI)

Listing 16.2.6.3 A-a Oxygen Gradient and Oxygenation Index (OI)

Listing 16.2.6.4 Blood Gas Analysis (BGA) (All Randomized)

Listing 16.2.6.5 Biomarkers of Inflammation in Tracheal Aspirates (All Randomized)

Listing 16.2.6.6 Respiratory Support/Duration of Ventilation (All Randomized)

Listing 16.2.6.7 Duration of Oxygen use Alone (All Randomized)

Listing 16.2.6.8 Assessment of Mortality and BPD (All Randomized)

### **ADVERSE EVENTS**

Listing 16.2.7.1 Pre Treatment Adverse Events (All Randomized)

Listing 16.2.7.2 Treatment-emergent Adverse Events (All Randomized)

Listing 16.2.7.3 Adverse Drug Reactions (All Randomized)

Listing 16.2.7.4 Serious Adverse Events (All Randomized)

Listing 16.2.7.5 Adverse Events Leading to Death (All Randomized)

Listing 16.2.7.6 Neonatal Complication of Prematurity (All Randomized)

